If they choose to continue using the implant they will be given the option to participate in the Home and Community Integration phase. They may then receive configurations for the behaviors and/or physiological

responses that were not in their assigned group interventions. They will participate in daily sessions identifying configurations for each of the other interventions that they did not receive during the study. Configurations will only be released to the research participant after being conducted safely in the laboratory and demonstrated by the research participant that they can safely implement the scES independently from the research staff. If the research participant would like to continue scES, they will be provided with stimulation configurations that were not part of their group interventions. This will require that they will stay in Louisville for approximately 8 additional weeks to undergo home and community integration of the stimulation parameters. The duration of stay will be variable and depend on the time it takes to identify effective configurations for each behavior and/or physiological response.

Follow up studies will be conducted at 6 months and 1 year. If an individual has removed the epidural stimulator, then the assessments will be done without stimulation only.

Follow up assessments will occur at 6 months and one year after post-interventions completion (Appendix #1).

5. Blood Draws for Laboratory Testing

Blood will be drawn at Screening, Pre-Usual Care, Pre-Implant, Post-Intervention #1, Post-Intervention #2, and Follow-Up time points to test for the following levels in the blood: lipid panel, fasting insulin, fasting glucose, complete metabolic panel, angiotensin, renin, aldosterone, leptin, interleukin 6, tumor necrosis factor alpha (TNF- α), plasminogen activator inhibitor 1 (PAI-1), complete blood count, GGT, c-reactive protein (CRP), erythrocyte sedimentation rate (ESR), albumin, procalcitonin, prealbumin, vitamin D, and trimethylamine-N-oxide (TMAO). Blood may be drawn prior to surgery to test for the following: complete blood count (CBC), basic metabolic panel (BMP), PT/PTT, and blood type and screen. Blood that will be drawn prior to surgery to test for infection is described below.

C. Specific Aims.

Specific Aim 1.

Understand the effect of epidural stimulation alone using specific configurations on outcomes for voluntary movement, cardiovascular function and independent standing.

Primary Analyses:

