Methods: Linear Statistical Models will be fit containing parameters for the main effect of each stimulation setting (Vol, CV, and Stand) and additive effects of weight bearing stand training for each stimulation setting. This hypothesis will be tested using the stand training coefficient corresponding to CV-scES. See section G for more details.

Specific Aim 3:

Understand the effects of scES alone and scES with stand training on respiratory, bladder, bowel and sexual function.

Secondary Analyses:

Hypothesis 3a: CV-scES selected for cardiovascular function will result in greater improvements in respiratory, bladder, bowel and sexual function than Vol-scES selected for voluntary movement

Rationale: We propose that CV-scES will further activate spinal autonomic circuitry and thus influence similar systems, respiratory, bladder, bowel and sexual function in addition to these mechanisms occurring with improvements in the cardiovascular system.

Methods: Linear Statistical Models will be fit containing parameters for the main effect of each stimulation setting (Vol, CV, and Stand) and additive effects of weight bearing stand training for each stimulation setting. This hypothesis will be tested using the contrasts between the stimulation settings both with and without weight bearing stand training. See Section G for more details.

Hypothesis 3b. CV-scES selected for cardiovascular function combined with task specific stand training using Stand-scES will result in greater improvement in respiratory, bladder, bowel and sexual function than CV-scES alone.

Rationale: Exercise programs involving limb muscles are known to increase fitness and improve ventilatory function in individuals with chronic SCI [81, 82]. However, none of the respiratory rehabilitative modalities have yet been proven to be clinically effective in patients with chronic SCI [83]. Preliminary results of locomotor training studies from our center indicate that the weight bearing step training in individuals with motor complete SCI leads to increased spinal motor output to respiratory muscles, but does not improve the voluntary initiated respiratory muscle activating patterns [84]. We have also found that weight-bearing exercise improves bladder function. Thus the combination of CV-scES with scES stand training will provide the greatest effect.

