The bladder will be imaged to assess for volume, thickness, and blood flow, evidence of distal ureteral obstruction, diverticula and for calculi. The bladder will be imaged from top to bottom and from side to side, in transverse and sagittal planes, respectively. Note that while a full bladder facilitates bladder scanning, distension may be a cause of artifactual hydronephrosis and is therefore to be avoided in scanning the kidneys.

Analysis: Analysis of kidney and bladder morphology, grades of hydronephrosis, the presence of masses, cysts and/or obstructions will be recorded by the radiologist and compared to prior evaluations. All exams will be reviewed with the study doctor.

6. Bowel

a. Bowel Questionnaire.

Procedure: The International Bowel Function Basic Spinal Cord Injury Data Set [146] will be used to assess bowel function. The items on the data set include awareness of need to defecate, defecation method and bowel care procedures, average time for defecation, frequency of defecation, frequency of fecal incontinence, and medications/oral laxatives used. The average time to defecation has been modified from the original data set to include a larger choice of times (smaller ranges). Participants will be asked to complete the questionnaire on the same day they present for either Urodynamics (when bladder and sexual function questionnaires are completed) or following Anorectal Manometry. The daily voiding diary will include a place to record the length of time for defecation, so that accurate data is collected and a time-line for any changes can be detected.

Analysis: Information recorded on the bowel function data set will be combined with results from the Anorectal Manometry procedure performed that day in order to provide a comprehensive assessment of the participant's bowel management at that particular intervention/time point. The average time required for defecation will be averaged across time points for each participant.

b. Anorectal Manometry (ARM).

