Appendix #1

Appendix 1. Frequency of Outcomes for Aims 1 – 3.

Assessment Category #=with and without stim	Assessments	Pre-screen	Screen	Pre-Usual Care	Pre-implant	Post-Implant/ Pre-Intervention	Weekly	Periodic Through Intervention	Monthly	Post-Intervention #1	Post-Intervention #2	Follow Up(s)
Medical	SC MRI	X	or X									
	ASIA		X	X	X					X	X	
	Physician and PT Medical		X	X	X					X	X	X
	Pregnancy	X	X									
	Blood Work		X	X	X					X	X	X
	Drug Testing	X	X	X	X	X	X	X		X	X	X
Voluntary	MMR		X									
	FNPA		X	X	X	X#				X#	X#	X#
	NRS trunk and leg score		X	X		X#		X#		X#	X#	X#
	Lower Extremity Torque with EMG					X#		X#		X#	X#	X#
	Neuromuscular Voluntary Movement Assessments					X#		X#		X#	X#	X#
Cardiovascular	Ambulatory BP monitoring		X	X				X	X	X	X	X
	Ambulatory HR monitoring		X	X				X	X	X	X	X
	12 lead ECG				X					X	X	
	Orthostatic Stress Test		X	X	X	X#		X#		X#	X#	X#
	Vascular Ultrasound			X	X	X#		X#		X#	X#	X#
	Echo-cardiography		X	X	X	X#		X#		X#	X#	X#
	Arterial pulse wave velocity		X	X	X	X#		X#		X#	X#	X#
	Sympathetic skin responses				X					X	X	
Stand	Dexa		X		X					X	X	X
	Independence levels during stand -			X	X	X#	X#	X#		X#	X#	X#
	Standing Assessments				X	X#		X#		X#	X#	X#
Respiratory	Pulmonary Function Test		X		X	X#				X#	X#	X#
	Respiratory Motor Control Assessment		X		X	X#				X#	X#	X#
	Resting metabolic rate		X	X	X					X	X	X

Assessment Category #=with and without stim	Assessments	Pre-screen	Screen	Pre-Usual Care	Pre-implant	Post-Implant/ Pre-Intervention	Weekly	Periodic Throughout Intervention	Monthly	Post-Intervention #1	Post-Intervention #2	Follow Up(s)
Bladder	Urodynamics		X	X	X					X	X	X
	Bladder Questionnaire			X	X					X	X	X
	Urinalysis			X	X					X	X	X
	Ultrasound			X	X					X	X	X
Bowel	Bowel Questionnaire			X	X					X	X	X
	Anorectal Manometry			X	X					X	X	X
Sexual Function	International Dataset (Males)			X	X					X	X	X
	International Dataset (Females)			X	X					X	X	X
Quality of Life	SCI-QOL		X		X					X	X	X
	SCI-FI		X		X					X	X	X
	PROMIS		X		X					X	X	X
	EQ-5D-3L		X		X					X	X	X

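### Defecation time is to be averaged across time points within each participant, which loses within-person change and dilutes between-arm contrasts for this one bowel item

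*Protocol*

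**What the plan says.** Section III.D.6.a of the Protocol describes the bowel questionnaire, which includes an item on average defecation time. Three statements there bear on the analysis:

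- The daily voiding diary also records how long defecation takes, "so that accurate data is collected and a time-line for any changes can be detected".
- Questionnaire answers are combined with that day's anorectal manometry to describe "bowel management at that particular intervention/time point".
- For defecation time itself: "The average time required for defecation will be averaged across time points for each participant".

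In Appendix 1 the row "Bowel Questionnaire" is marked at Pre-Usual Care, Pre-implant, Post-Intervention #1, Post-Intervention #2 and Follow Up(s). Section III.B.4 fixes the last column: "Follow up assessments will occur at 6 months and one year after post-interventions completion".

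Specific Aim 3 is to "Understand the effects of scES alone and scES with stand training on respiratory, bladder, bowel and sexual function". Its two hypotheses are comparative. Under 3a, "CV-scES selected for cardiovascular function will result in greater improvements in respiratory, bladder, bowel and sexual function than Vol-scES". Under 3b, CV-scES combined with stand training "will result in greater improvement in respiratory, bladder, bowel and sexual function than CV-scES alone".

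Section III.G gives the model for secondary endpoints. It has one coefficient per stimulation setting and one for added stand training within each setting, and each is switched on only for the treatment received.

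**The concern.** The time points over which the rule averages lie on both sides of treatment. Two precede the implant. The others follow the first intervention, the second intervention and the end of the programme. One mean over all of them cannot show whether a participant's defecation time fell, rose or stayed the same.

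The crossover adds to this. A participant who starts in A2 has CV-scES alone in period 1 and CV-scES with stand training in period 2. Hypothesis 3b compares those two conditions, and the rule puts both into one number.

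At stake is the usefulness of defecation time as evidence for 3a and 3b. An SAP that follows the sentence inherits the problem. One that departs from it contradicts the Protocol.

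**Working it through.** The Protocol gives no figure to reproduce for this item. The check compares the texts and then works out what the averaging does.

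**1. Number of time points.** Appendix 1 gives Pre-Usual Care, Pre-implant, Post-Intervention #1 and Post-Intervention #2, which is 4. Section III.B.4 adds follow-up at 6 months and 1 year, which is 2. So K = 4 + 2 = 6, and 2 of the 6 precede any stimulation.

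**2. Within-person change.** Leave follow-up aside and take three assumed courses in minutes, for illustration only:

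- improved: (60 + 60 + 30 + 30)/4 = 45
- worsened: (30 + 30 + 60 + 60)/4 = 45
- unchanged: (45 + 45 + 45 + 45)/4 = 45

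All three give the same value, so the direction of change is gone as well as its size.

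**3. Between-arm contrast.** If d_k is the true difference between two arms at visit k, the difference between their across-visit means is (1/K) × Σ d_k. With K = 6 and a difference D at the affected visits:

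| Where D is present | Contrast in means | Share of D |
|---|---|---|
| one visit | D/6 | 17% |
| both post-intervention visits | 2D/6 | 33% |
| both post-intervention visits and both follow-ups | 4D/6 | 67% |

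If follow-up is left out of the average (K = 4), the first two rows become D/4 (25%) and 2D/4 (50%).

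**4. Worked example, six visits.** Assumed values: baseline 60; CV-scES lowers the time by 20; stand training lowers it by a further 10; Vol-scES has no effect; effects persist through follow-up.

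- A2: 60, 60, 40, 30, 30, 30; sum 250, mean 41.67
- B2: 60, 60, 30, 30, 30, 30; sum 240, mean 40.00
- A1: 60, 60, 60, 50, 50, 50; sum 330, mean 55.00

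For 3b, B2 minus A2 at Post-Intervention #1 is 30 − 40 = −10. In the means it is 40.00 − 41.67 = −1.67, one sixth. This is the one-visit case, because Group A also has stand training in period 2.

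For 3a, A2 minus A1 at Post-Intervention #1 is 40 − 60 = −20. In the means it is 41.67 − 55.00 = −13.33, four sixths.

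Within A2, the change from Pre-implant to Post-Intervention #2 is 30 − 60 = −30, and the step on adding stand training is 30 − 40 = −10. Neither can be read from 41.67.

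**5. Fit with section G.** For an A2 participant the model needs a period 1 response explained by the CV-scES coefficient alone, and a period 2 response explained by that coefficient plus the one for stand training within CV-scES. A single mean over six visits belongs to neither. For a B2 participant the treatment is the same in both periods, but 2 of the 6 values averaged are still untreated.

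**6. Fit with neighbouring outcomes.** In section III.D.5, urodynamic values are compared with previous time points and ultrasound findings with prior evaluations. No text in the Protocol confines the defecation-time average to entries within one visit or period.

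**The case against.** The best reply is that the sentence is a drafting slip in a descriptive paragraph and not the rule for testing 3a and 3b. Those tests are set in section G and the Aim 3 methods, which need a value per period and allow subject random effects and a first-period sensitivity analysis. The sentence just before the averaging rule refers to a particular intervention or time point, so the authors may have meant to average within each time point. That is plausible. It does not remove the point, because the sentence says something else and no other text overrides it.

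Three stronger readings are tempting, and the Protocol does not support them.

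- A reader might infer that the change in bowel function under Aim 3 is lost altogether. It is not. The rule covers one item. Awareness of need, method, frequency, incontinence and medication, and all anorectal manometry measures, are not averaged across visits.
- A reader might infer that 3a and 3b cannot be tested on defecation time. The Protocol never names the across-visit mean as the response for those hypotheses, values are collected at every time point, and between-arm contrasts would be diluted, not erased.
- A reader might take the one-sixth share as the loss of power. It is the loss of signal only. A mean of several visits also carries less within-person noise, and the Protocol gives no variances with which to set one against the other.

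It also stands that this is one item of a secondary instrument and that no primary hypothesis (1a to 1c) depends on it.

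**Conclusion.** The point holds, for average defecation time only. As written, the rule gives one value per participant over six time points, removes within-person change entirely, and reduces a between-arm difference D to between D/6 and 4D/6, depending on where the difference is present. It contradicts the purpose stated in its own section and does not fit the section G model.

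The shares assume that all six visits are attended and equally weighted. The 4D/6 case also assumes that the effect lasts through both follow-ups. That is uncertain, since participants may by then have had the stimulator removed or received configurations outside their assigned group (sections III.B.4 and III.F). The minutes in the example are invented for illustration.

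Nothing is irrecoverable. This is a stated rule that needs correcting, with limited reach.

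**What to change.** Replace the averaging sentence in section III.D.6.a with:

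> Defecation time will be summarised separately at each assessment time point for each participant (Pre-Usual Care, Pre-implant, Post-Intervention #1, Post-Intervention #2 and each follow-up) and compared between time points; it will not be averaged across time points. If diary entries are used, they will be averaged only within the period belonging to each time point.

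Use the post-intervention value for each period as the section G response for 3a and 3b, and the change from Pre-Usual Care to Pre-implant to describe Usual Care.

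The cost is a short change of wording. The questionnaire item is already scheduled at every time point, so no visit, measurement or participant is added. The one extra task arises if the diary is used: it is kept daily and has no row in Appendix 1, so the span of entries belonging to each time point must be defined.

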Each participant begins 80 sessions of Usual Care to obtain baseline levels, followed by two intervention periods. In the first intervention period (intervention 1, at least 80 sessions), participants will be randomized to one of the four different interventions (A1, A2, B1, or B2). Each research participant will complete at least 80 sessions of the intervention to which they are randomized. At the completion of at least 80 sessions of intervention 1, clinical and neurophysiological assessments will be conducted (Appendix #1). Some assessments may be completed more often.

At the conclusion of the first intervention period, a second intervention period of at least 80 sessions will be commenced. During this second intervention period, participants that had not been receiving weight bearing stand training will be crossed over to receive it. Participants who had been receiving weight bearing training will repeat their current intervention. Thus, participants who had A1 or A2 in intervention 1 would cross over to B1 or B2, respectively, while participants who had B1 or B2 would repeat their intervention.

In what follows it is often convenient to refer to groups (the specific cohort of 9 participants) by their initial intervention in period 1, thus we will refer to groups as A1, A2, B1, or B2, as appropriate.

After at least 80 sessions of the second intervention are completed, assessments are conducted. If an individual does not complete at least 80 sessions of their assigned group intervention, their data will still be evaluated.

Table 1. Interventions for research participants (n=36)

(n=18) Group A		(n=18) Group B	
Intervention #1			
N=9 A1 Vol- scES 6 hours	N=9 A2 CV-scES 6 hours	N=9 B1 Vol-scES 6 hours and Stand-scES + weight bearing training 2 hours	N=9 B2 CV-scES 6 hours and Stand-scES + weight bearing training 2 hours
Intervention #2			
B1 Vol-scES 6 hours and Stand-scES + weight bearing training 2 hours	B2 CV-scES 6 hours and Stand-scES + weight bearing training 2 hours	B1 Vol-scES 6 hours and Stand-scES + weight bearing training 2 hours	B2 CV-scES 6 hours and Stand-scES + weight bearing training 2 hours
Home and Community Integration			

Appendix #1 gives a detailed outline for the timeline and procedures for an individual research participant.

The research participant will be given the choice to have the implant removed by the study neurosurgeon. The neurosurgeon will remove the stimulator if requested by the research participant.

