Hypothesis 1a: Primary Efficacy Hypothesis: CV-scES will result in greater cardiovascular functional improvements than those achieved during Usual Care Intervention.

Hypothesis 1b: Secondary Efficacy Hypothesis: Task specific voluntary movement training using Vol-scES will result in greater improvements in voluntary movement than those achieved during Usual Care Intervention.

Hypothesis 1c: Secondary Efficacy Hypothesis: Stand Stand-scES (parameters optimized for standing) will result in greater improvements in the ability to stand than those achieved during the Usual Care Intervention.

Secondary Analyses:

Hypothesis 1d: Task specific voluntary movement training using Vol-scES (parameters optimized for voluntary movement) will result in more successful voluntary movements than CV-scES.

Rationale: We propose that the spinal circuitry is the key integrator of complex signals from the periphery and supraspinal centers that drive the final motor pool output. We predict that the circuitry is continuously adapting to activity-dependent events that functionally configure the spinal networks to optimize generation of a specific motor task. Other possibilities are that the scES retrogradely stimulates residual axons that anatomically cross the lesion but are not functional, or, that scES restores the conduction properties that are lost with demyelination or other consequences of damage [2, 70, 73-76]. If only the restoration of the conduction of the residual supraspinal connections are needed, then the scES **alone** without voluntary training should be sufficient to restore voluntary movement of the legs. However, if the spinal cord circuitry is a key controller, then task specific training of voluntary movement in the presence of scES would also be required to optimally generate voluntary movement.

Methods: Linear statistical models will be fit with coefficients relating to the three stimulation methods. This hypothesis will be tested by if the Vol-scES estimates are significantly higher than those for CV-scES or Stand-scES stimulation parameters. See Section G for details.

Hypothesis 1e: CV-scES (parameters optimized for cardiovascular function) will result in greater cardiovascular functional improvements than Vol-scES.

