Rationale: We propose that scES, when optimized for cardiovascular function to normalize blood pressure and reduce the severity of orthostatic hypotension will result in improvements of cardiovascular function. We hypothesize the number and severity of hypotensive episodes will be reduced (i.e. restored sympathetic drive), which will thereby inhibit the accelerated arteriosclerosis observed in the central vasculature of those with SCI and reduce cardiovascular disease risk [16, 17]. We anticipate that scES optimized for cardiovascular function will activate spinal sympathetic circuitry and increase vascular tone and consequently blood pressure to 'load' the heart in a similar way to that of mechanical compression of the abdomen.

Methods: Linear statistical models will be fit with coefficients relating to the three stimulation methods. This hypothesis will be tested by if the CV-scES estimates are significantly higher than those for Vol-scES or Stand-scES stimulation parameters. See Section G for details.

Hypothesis 1f: Stand-scES (parameters optimized for standing) will result in improvements in the ability to stand without physical assistance than Vol-scES or CV-scES.

Rationale: It is also plausible that scES optimized for stand training may activate lower limb musculature to a sufficient degree that standing without physical assistance will occur even without weight-bearing training. The scES for cardiovascular would not activate the lower limb musculature. The scES for voluntary trunk and leg movements would not activate the lower limb musculature in a manner that would promote standing if task-specificity is important for the recovery.

Methods: Linear statistical models will be fit with coefficients relating to the three stimulation methods. This hypothesis will be tested by if the Stand-scES estimates are significantly higher than those for Vol-scES or CV-scES stimulation parameters. See Section G for details.

Specific Aim 2.

Understand the effect of epidural stimulation in combination with stand training on outcomes for voluntary movement, cardiovascular function and independent standing.

Secondary Analyses:

Hypothesis 2a: Task specific voluntary training using Vol-scES combined with task specific stand training using Stand-scES will result in more successful voluntary movement than voluntary training using Vol-scES alone.

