Rationale: Stand training (weight-bearing training with dynamic assistance) with simultaneous Stand-scES may also be required for the recovery of voluntary movement, given that the nervous system evolved in an anti-gravity environment and information related to load bearing has been shown to be a critical factor in modulation of neural activity [77-79]. Astronauts and research animals who are neurally intact return to earth with neural disorders such as spasticity and clonus that are common to individuals with spinal cord injury [80], indicating that loss of load related sensory information drives neural plasticity that results in deleterious effects. Due to these insights and others, we believe that the most efficacious approach to restoration of voluntary movement is to combine scES with voluntary training and scES with stand training.

Given that each of our subjects to date has received stand training with Stand-scES as well as training for voluntary movement of the limbs with Voluntary-scES, it may require the combination of both to recover and improve voluntary movement. To some degree, even when standing, there is undoubtedly some critical element of voluntary control of posture and balance, so there may be overlap of circuitries controlling standing and voluntary movement. In testing this hypothesis we will determine whether there can be complementary effects of stand and voluntary leg movement training, or whether stand or voluntary training is necessary.

Methods: Linear Statistical Models will be fit containing parameters for the main effect of each stimulation setting (Vol, CV, and Stand) and additive effects of weight bearing stand training for each stimulation setting. This hypothesis will be tested using the stand training coefficient corresponding to Vol-scES. See section G for more details.

Hypothesis 2b: CV-scES (parameters optimized for cardiovascular control) combined with task specific stand training using ES parameters selected for stand training will significantly improve blood pressure control along with cardiac and cerebral function to a greater extent than ES optimized for CV alone.

Rationale: We propose that muscle activation with Stand training (weight-bearing training with dynamic assistance) with Stand-scES will further activate spinal sympathetic circuitry and increase vascular tone and thus blood pressure in addition to these mechanisms occurring with CV-scES.

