For those participants not achieving independent standing during the stand training phase of the protocol, the home and community integration will include training in a customized standing device. Standing devices will be designed to match the level of assistance required to safely translate the training to the home environment. This phase can also include training of care givers or personal trainers to assist the participants in achieving safe and independent standing.

G. Statistical approaches.

For the primary aims (comparing to baseline), paired sample t-tests will be used the primary endpoints (hypotheses 1a, 1b, 1c) comparing the results at the end of the second intervention period to the baseline period.

For the secondary aims, each endpoint will be analyzed separately with a common linear model framework. We fit a linear model with effects for each stimulation setting (voluntary, cardiovascular, and standing) and an effect of weight bearing stand training within each stimulation setting. Thus, for example we have a coefficient which measures the additional benefit of weight bearing stand training and a stimulation setting over and above that stimulation setting alone. There are separate coefficients for the benefit of stand training within Vol-scES, CV-scES, and Stand-scES. Formally, we fit a linear model of the form

$$\begin{aligned} \text{Response} = & \beta_{\text{Vol-scES}} I_{\text{Vol-scES}} + \beta_{\text{CV-scES}} I_{\text{CV-scES}} + \beta_{\text{Stand-scES}} I_{\text{Stand-scES}} + \\ & \beta_{\text{VT}} I_{\text{Vol-scES and Training}} + \beta_{\text{CVT}} I_{\text{CV-scES and training}} + \\ & \beta_{\text{ST}} I_{\text{Stand-scES and training}} + \text{error} \end{aligned}$$

where the β terms give the regression coefficients and I_X is an indicator variable equal to 1 if X occurs and 0 otherwise. The indicator variables function to only include the coefficients of the model for treatments the participant actually receives. Thus, for a participant receiving CV-scES and stand training, the model would reduce to

$$\text{Response} = \beta_{\text{CV-scES}} + \beta_{\text{CVT}} + \text{error}$$

Due to the partial crossover, no carryover effects are included in the model (sensitivity analyses using only the first period data will also be summarized). Random effects for each subject may be included when appropriate.

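### Hypotheses 1a and 1b are tested at the end of intervention period 2, when every participant also receives Stand-scES with weight-bearing training, so the tests cannot support Aim 1's conclusion about stimulation alone

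*Protocol*

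**What the plan says.** Specific Aim 1 (Protocol III.C) reads "Understand the effect of epidural stimulation alone using specific configurations on outcomes" for voluntary movement, cardiovascular function and standing. Under its heading "Primary Analyses" come hypotheses 1a to 1c. Hypothesis 1a, labelled the primary efficacy hypothesis, states that "CV-scES will result in greater cardiovascular functional improvements than those achieved during Usual Care Intervention". Hypothesis 1b makes the parallel claim for voluntary movement training with Vol-scES.

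Specific Aim 2 is separate: "Understand the effect of epidural stimulation in combination with stand training on outcomes for voluntary movement, cardiovascular function and independent standing".

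Section III.G assigns paired t-tests to 1a, 1b and 1c, "comparing the results at the end of the second intervention period to the baseline period". On the design, III.B.4 says: "During this second intervention period, participants that had not been receiving weight bearing stand training will be crossed over to receive it". A1 therefore moves to B1 and A2 to B2, while B1 and B2 repeat their regimen. The linear model, with separate terms for stimulation and for added stand training, is introduced in III.G for the secondary aims. So is its sensitivity analysis on first-period data.

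The labels also disagree. III.C heads 1a to 1c as primary analyses and III.G calls them primary endpoints, but the text reads "Hypothesis 1b: Secondary Efficacy Hypothesis", and 1c carries the same label.

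**The concern.** The primary efficacy test is read at a time when the component that Aim 1 sets aside has been added for everyone. The protocol does not regard that component as inert. The rationale for 2a says that "the most efficacious approach to restoration of voluntary movement is to combine scES with voluntary training and scES with stand training". The rationale for 2b expects stand training with Stand-scES to raise blood pressure beyond what CV-scES does. A positive result on 1a or 1b could therefore come from CV-scES or Vol-scES, from Stand-scES with weight-bearing training, or from both, and the paired test cannot tell which. Reported under Aim 1, it would be taken as evidence for stimulation alone.

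**Working it through.** **1. Regimen at each assessment** (III.B.4 and Table 1, 9 participants per cohort).

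| Cohort | Post-Intervention #1 | Post-Intervention #2 |
|---|---|---|
| A1 (9) | Vol-scES | Vol-scES + Stand-scES with training |
| A2 (9) | CV-scES | CV-scES + Stand-scES with training |
| B1 (9) | Vol-scES + Stand-scES with training | same |
| B2 (9) | CV-scES + Stand-scES with training | same |

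Without stand training: 9 + 9 = 18 of 36 at Post-Intervention #1, and 0 of 36 at Post-Intervention #2.

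**2. What the test estimates.** In III.G's own model, a participant on CV-scES with stand training has expected response β_CV-scES + β_CVT. The corresponding sum for Vol-scES is β_Vol-scES + β_VT. At the tested time point only these sums are observed. Stimulation alone corresponds to the first term by itself, which is observed only in A2 (for 1a) and A1 (for 1b) in period 1.

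**3. Which analyses separate the terms, and for what.** III.G assigns the contrasts between stimulation settings to 1d, 1e, 1f, 3a and 3b, and the stand-training coefficients to 2a, 2b and 2c. None is assigned to 1a or 1b.

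**4. What a stimulation-alone reading would risk.** The protocol gives no effect sizes for this, so the range is assumed. Suppose stimulation alone did nothing and stand training shifted the outcome by d SD of the paired change. Rejection probability of the paired test at 0.05 is 1 − F(t_crit; n−1, d√n), where F is the noncentral t distribution function.

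| d | n=18 one-sided | n=18 two-sided | n=9 one-sided | n=9 two-sided |
|---|---|---|---|---|
| 0.25 | 27% | 17% | 17% | 10% |
| 0.50 | 65% | 52% | 39% | 26% |
| 0.75 | 92% | 85% | 66% | 51% |

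These rejections are correct for the combined regimen. They would be wrong only as statements about stimulation alone.

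**5. Price of testing before crossover.** The protocol's only power figure (90% for an effect size of 1.7, one-sided 0.05) concerns comparisons between stimulation settings. It reproduces with 6 per group and the normal approximation: 1.7 × √(6/2) − 1.645 = 1.30, or 90.3%. It says nothing about the paired tests, and III.G gives no sidedness for them, so both are shown. The change detectable with 90% power solves 1 − F(t_crit; n−1, d√n) = 0.90:

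| | t_crit, n=9 | d, n=9 | t_crit, n=18 | d, n=18 |
|---|---|---|---|---|
| One-sided 0.05 | 1.860 | 1.07 | 1.740 | 0.72 |
| Two-sided 0.05 | 2.306 | 1.24 | 2.110 | 0.81 |

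At the change that 18 participants detect with 90% power, 9 participants have 63% power one-sided (d√n = 0.719 × 3 = 2.16) or 57% two-sided (0.811 × 3 = 2.43). The 18 assumes pooling A2 with B2, or A1 with B1. The protocol does not say which participants enter each paired test.

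**The case against.** The best defence is that the word alone belongs to Aim 1 and not to 1a or 1b. The aim does not use it strictly either: 1b includes voluntary training, and 1c concerns Stand-scES, which is never given without weight-bearing training. If 1a and 1b mean any regimen containing CV-scES or Vol-scES against baseline, the period-2 test answers them. This stands as a limit on the point. It does not remove it, because Aim 2 separately holds the combination and 1a and 1b are placed under Aim 1.

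A reader might infer more than the protocol supports:

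- **That the paired test is invalid.** It is a valid test of the combined regimen against baseline. The mismatch is between the stated aim and what the test estimates.
- **That stimulation alone is never analysed.** The linear model has terms for it, the first-period sensitivity analysis isolates it, and III.G describes contrasts for it. What is missing is any assignment of these to 1a or 1b.
- **That 1c is tested at the wrong time.** Period 2 suits it, since Stand-scES comes only with weight-bearing training. It is 1c's place under an aim about stimulation alone that does not fit.
- **That the echocardiography t-test in III.D.2.c has the same fault.** That section compares baseline with the end of training. It neither defines the end of training as period 2 nor ties the test to 1a, so this can be raised only conditionally.

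A statistical analysis plan might add detail. The protocol itself, however, already fixes the test, the hypotheses and the time point.

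**Conclusion.** The point holds as a mismatch between Aim 1 and the analysis set for 1a and 1b. Its size is the count: 0 of 36 participants on stimulation without stand training at the tested time point, against 18 of 36 one assessment earlier. The counts rest on Table 1 and on participants following the planned crossover. The SD figures price one of the remedies and do not measure the defect. They also depend on the assumed pooling. Because 1a is the primary efficacy hypothesis, the mismatch should be resolved before analysis. The conflicting primary and secondary labels on 1b and 1c are a minor, separate inconsistency.

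**What to change.** Choose one.

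**Option 1: move the test.** Test 1a in A2 and 1b in A1 at Post-Intervention #1, and report the period-2 test as the combined-regimen effect. Name one pre-intervention assessment per outcome as baseline, and state whether stimulation is on or off for the follow-up value as well as for the baseline value. Appendix 1 already schedules:

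- a pre-implant assessment for the orthostatic stress test, echocardiography, pulse wave velocity and FNPA;
- a post-implant, pre-intervention assessment for NRS, lower-extremity torque and neuromuscular voluntary movement. This falls after Usual Care, which III.B.4 makes the source of baseline levels, so the text should say so.

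Among these voluntary and cardiovascular outcomes, only ambulatory blood pressure and heart rate have neither mark. Reconcile Appendix 1 with III.B.2 and III.B.3 before naming their visit. The cost is wording plus one named baseline per outcome, with no new visit, allocation or data collection, and the loss of precision shown in the working.

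**Option 2: keep the test.** Reword Aim 1, 1a and 1b so that their conclusion concerns stimulation combined with Stand-scES and stand training. The cost is wording only, but 1a and 1b then make no claim about stimulation alone.

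**Under either option:**

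- Keep 1c at period 2, and state that it concerns Stand-scES with weight-bearing training and so cannot fall under stimulation alone.
- If the end of training in III.D.2.c means the end of period 2 and that test is used for 1a, make it agree with the option chosen.
- Reconcile the primary headings in III.C and III.G with the secondary labels on 1b and 1c.
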